4.7 Variables/Measures

The primary outcome of interest is COVID-related hospitalization rate in study participants and matched controls. We list all potential covariates in two phases. Phase I covers historical data and Phase II includes post COVID-19 diagnosis information. Phase I historical data will be

collected for both study participants and matched controls. Phase II post-COVID 19 diagnosis data has two parts: data elements to be collected for both study participants and matched controls (Phase II.A), and data elements to be collected for only study participants (Phase II.B).

Phase I - Historical data: Study participants and matched controls:

1. COVID-19-related information:

Variable	Data source for study participants	Data source for matched controls
Date of COVID-19 diagnosis test	ProtectWell	Optum EMR or CDSM
Type of COVID-19 diagnosis test*		
Symptomatic flag during COVID-19 test	ProtectWell (all study participants are symptomatic)	Optum EMR
Previous COVID diagnosis flag	CDSM	Optum EMR or CDSM
Previous receipt of Bamlanivimab	UHC claims	Optum EMR or UHC Claims

*: Please see Table A1 in Appendix 1 for LOINC codes of the PCR and antigen COVID-19 tests.

Commented [WWY15]: This variable won't be used for analysis.

Commented [JAT16R15]: Not necessarily. We'll use it to approximate date of symptoms onset and identify matched controls who got COVID-19 around the same time. Please see the comment below for more details.

Commented [WWY17]: Would also include COVID-19 symptoms, and a timing variable: duration since symptom onset to index date

Commented [JAT18R17]: We will include these data fields if available. Regarding date of symptoms onset, it's approximated to be 2 days prior to date of COVID-19 diagnosis (1 day for overnight shipping of COVID-19 test kit and the other day for PCR test).

2. Demographic:

Variable	Data source for study participants	Data source for matched controls
Age as of 2021*		
ZIP code of residence (may or may not be used for identifying matched controls)		
Urbanization of residence in a zip code level (urban, suburban, rural)		
Region/State of residence		
Race		
Gender		
Flag determining whether a patient resides in a nursing facility – determining a patient does not live at home		

*: Age = 2021 – birth year.

Commented [WWY19]: As obesity is a high risk factor, suggest to include BMI as a covariate in PS matching

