5.12 Other Analyses

Objective:	Data Variables:	Data Source:
Evaluate the association of the time gap between a COVID positive test result and an infusion with COVID hospitalization	
• Date of symptoms onset• Date of COVID diagnosis• Date of infusion treatment• Date of COVID hospitalization• Demographics• Elixhauser conditions	
• Optum infusion pharmacy data• UHC claims data• CDSM COVID labs data• ProtectWell data
Evaluate the association of the time gap between a symptom onset and an infusion with COVID hospitalization		

There are two pre-specified analyses we will pursue aside from the primary, exploratory and safety objectives in the previous sections.

First, we want to understand if the timing of the infusion relative to a positive COVID test, impacts hospitalizations. We will compute the Cramer's V and phi coefficient as one-number summary of correlation between two categorical variables when we group time gap between date of COVID positive and date of home infusion. If considering this time gap as a continuous variable, we will run a simple logistic regression model to examine if time gap is associated with the hospitalization rate at Day 28. Then, we will apply the same methodology described above for categorical and continuous covariates and binary outcomes.

Second, we want to understand if the timing of the infusion relative to a symptom onset, impacts hospitalizations. We will compute the Cramer's V and phi coefficient as one-number summary of correlation between two categorical variables when we group time gap between date of COVID positive and date of home infusion. If considering this time gap as a continuous variable, we will run a simple logistic regression model to examine if time gap is associated with the hospitalization rate at Day 28. Then, we will apply the same methodology described above for categorical and continuous covariates and binary outcomes.

CONFIDENTIAL

[Protocol number: UHG (J2X-NS-I002)] SAP [\[v.3\]](#)

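### The second timing analysis asks about symptom onset to infusion, but its method text uses the positive-test-to-infusion gap and so repeats the first analysis

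*SAP*

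**What the plan says.** SAP 5.12 sets out two timing questions. The first reads: "First, we want to understand if the timing of the infusion relative to a positive COVID test, impacts hospitalizations". The second reads: "Second, we want to understand if the timing of the infusion relative to a symptom onset, impacts hospitalizations". For each, the plan computes Cramer's V and the phi coefficient on a grouped gap, and then says: "we will run a simple logistic regression model to examine if time gap is associated with the hospitalization rate at Day 28".

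The grouped gap is described in the same words in both paragraphs: "group time gap between date of COVID positive and date of home infusion". The continuous version points back to that gap: "If considering this time gap as a continuous variable, we will run a simple logistic regression model".

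The table at the head of SAP 5.12 does separate the two questions. Its second objective is "Evaluate the association of the time gap between a symptom onset and an infusion with COVID hospitalization", and its variables include "Date of symptoms onset".

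Protocol 6.5.6 has the same two paragraphs with the same exposure wording. Its table is less complete: the only timing question there concerns the positive test, and no onset date appears among its variables.

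On how onset would be dated, a margin reply in SAP 4.7 says it is "approximated to be 2 days prior to date of COVID-19 diagnosis". The data collection lists (SAP 4.2, Protocol 6.4) start at the first symptom report, made through ProtectWell.

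**The concern.** The second analysis states one exposure in its question and a different one in its method. An analyst who programs from the method text would produce the first analysis again under a second label, and the onset-to-infusion question would go unanswered without anything in the output showing it.

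Onset to infusion is the timing measure closest to the study's own clock. The ten-day infusion window is counted from symptoms (onset in Protocol 6.1, report in Protocol 4.2), and the controls' synthetic treatment date is drawn from the participants' distribution of days since onset. Losing this result would leave the study without its planned look at timing on that scale.

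**Working it through.** The documents give no figure to reproduce here. The check is a comparison of text, followed by a short piece of algebra on the onset approximation.

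**Step 1. The two method paragraphs side by side (SAP 5.12; the same in Protocol 6.5.6).**

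| Element | First analysis | Second analysis |
|---|---|---|
| Question | Positive test to infusion | Symptom onset to infusion |
| Grouped exposure in method | Positive test to infusion | Positive test to infusion |
| Continuous exposure in method | The same gap | The same gap |
| Association measures | Cramer's V, phi | Cramer's V, phi |
| Model | Simple logistic regression | Simple logistic regression |
| Outcome | Hospitalization at Day 28 | Hospitalization at Day 28 |

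After the opening sentence, the two paragraphs are identical word for word. Same exposure, outcome, method and participants give the same result.

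**Step 2. What the tables say.** The SAP table names both gaps and lists the onset date. The protocol table names only the positive-test gap. The intended exposure can therefore be read from the SAP table, but in the protocol only from the opening sentence of the second paragraph.

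**Step 3. Would correcting the words be enough?** That depends on how onset is dated. Let I be the infusion date, D the diagnosis date and O the onset date. The test gap is T = I − D and the onset gap is S = I − O.

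If O = D − 2, as in the margin reply, then S = I − (D − 2) = T + 2 for every participant. In a logistic model,

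logit(p) = a + bS = (a + 2b) + bT.

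The slope b, its standard error and its p-value are the same for both gaps. Only the intercept moves, by −2b when T is replaced by S.

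**Step 4. Numerical illustration on assumed data.** The documents give no lag distribution, so these inputs are assumptions: 1,000 participants, onset to test 0–5 days, test to infusion 1–4 days, true log-odds −3 + 0.2 per day from onset.

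| Exposure in simple logistic model | Intercept | Slope | SE | p |
|---|---|---|---|---|
| Test gap T | −2.5201 | 0.2212 | 0.0851 | 0.0094 |
| Onset set to diagnosis minus 2 (T + 2) | −2.9625 | 0.2212 | 0.0851 | 0.0094 |
| Observed onset gap | −2.9329 | 0.1876 | 0.0481 | 0.0001 |

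The intercept shift agrees with the algebra: −2.5201 − 2 × 0.2212 = −2.9625. With an observed onset date the exposure is a different variable (correlation with T of 0.56 in these data) and the analysis is distinct. The values in the third row depend on the assumed lags. The equality of the first two rows does not.

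**The case against.** The best reply is that the intent is plain on the same page. The SAP table states the onset-to-infusion gap, lists the onset date and names ProtectWell as a source, so a careful analyst would notice the slip. That stands for the SAP, and it rules out the reading that the onset question is lost beyond recovery. It does not make the method text right, and the protocol has no such table entry.

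The reply on weight also stands. The analysis sits outside the primary, exploratory and safety objectives, and SAP 5.1 allows that not every analysis described will be performed.

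Three stronger readings may tempt a reader, and the documents do not support them:

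- **That the two-day rule is a second error.** It appears only in a margin reply, which promises the onset fields if they are available. The body of SAP 5.12 lists onset and diagnosis dates separately. The reply's reasoning (one day for kit shipping, one for the PCR test) does describe the participants' home-testing route, so a caution is fair, but no more than that.
- **That the two-day rule would make the grouped analyses identical.** This holds only if the cut-points also move by two days. Neither document gives cut-points. If, say, five days were used for both gaps, a participant with T = 4 and S = 6 would change group, and Cramer's V could differ.
- **That both timing models are wrongly unadjusted.** The word for a one-covariate model is used, but the paragraph then refers to the methods given earlier for covariates, and SAP 5.2 sets a default covariate list for logistic models in the efficacy analysis. Whether that default reaches SAP 5.12 is unclear, so absence of adjustment is not established.

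**Conclusion.** The exposure in the second timing analysis is wrong as written, in both SAP 5.12 and Protocol 6.5.6. Run literally, the second analysis duplicates the first in full. This rests on the text alone and needs no assumption.

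Severity is low. One additional analysis is affected, and its intended exposure can be recovered from the SAP table.

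The caution about dating onset is conditional. If the diagnosis-minus-two-days rule were applied to participants, the corrected logistic analysis would have the same slope and p-value as the first. If an observed date is used, it would not.

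**What to change.** 1. In the second paragraph of SAP 5.12 and of Protocol 6.5.6, define the exposure as infusion date minus symptom-onset date, for both the grouped and the continuous version.
2. Add the onset-to-infusion question, and the onset date as a variable, to the table in Protocol 6.5.6, so that it agrees with the SAP table.
3. State that the participants' onset date is the date of the first symptom report in ProtectWell, and that this is a report date standing in for onset. It may fall after true onset, and the text should say so.
4. State that the approximation of onset from the diagnosis date is not used for this analysis.

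The cost is wording in two documents. The first symptom report is already the first data collection timepoint, and ProtectWell is already a listed source for this analysis, so no new data collection is implied. That assumes the report date is in practice complete for infused participants, which the documents do not confirm.

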5.13 Interim Analyses

We plan to report descriptive statistics when we get the first 1,000 study participants and then conduct the primary analysis when we obtain the data through Day 28 for these study participants.

5.14 Changes to Protocol-Planned Analyses

NA.

LY3819253

6. Supporting Documentation

6.1 Appendix 1: Definitions and Medical Codes

1. COVID-19 tests: We list all LOINC codes of PCR or antigen COVID-19 tests we use to extract test result.

Table A1. LOINC codes of PCR/antigen COVID-19 tests.

Test type (PCR or antigen)	LOINC code
Antigen	95209-3 94558-4
PCR	94759-8 94534-5 94559-2 94316-7 94565-9 94533-7 94819-0 94760-6 95425-5 95608-6 94639-2 94756-4 94315-9 94309-2 94500-6 94308-4 95406-5

	94306-8
	94531-1
	95422-2
	95423-0
	95380-2
	94532-9
	94502-2

2. Elixhauser conditions: We list the 29 Elixhauser conditions in Table A2. The crosswalk of each condition and ICD-10 codes is on [the AHRQ website](#). We follow the AHRQ's definition to calculate the Elixhauser comorbidity score (Moore, 2017).

Table A2. The 29 Elixhauser conditions.

Elixhauser condition	
Acquired immune deficiency syndrome	Lymphoma
Alcohol abuse	Fluid and electrolyte disorders
Deficiency anemia	Metastatic cancer
Rheumatoid arthritis/collagen vascular diseases	Other neurological disorders
Chronic blood loss anemia	Obesity
Congestive heart failure	Paralysis
Chronic pulmonary disease	Peripheral vascular disorders
Coagulopathy	Psychoses
Depression	Pulmonary circulation disorders
Diabetes, uncomplicated	Renal failure
Diabetes with chronic complications	Solid tumor without metastasis

Drug abuse	Peptic ulcer disease excluding bleeding
Hypertension (combine uncomplicated and complicated)	Valvular disease
Hypothyroidism	Weight loss
Liver disease	

3. Immunosuppressive prescriptions: We identify immunosuppressive treatment by the following prescriptions in our claims data.

Table A3. The list of immunosuppressive prescriptions.

Immunosuppressive prescriptions

Cyclosporine	Abatacept
Tacrolimus	Etanercept
Sirolimus	Adalimumab
Everolimus	Infliximab-abda
Mycophenolate mofetil	Infliximab-dyyb
Mycophenolate sodium	Infliximab
Methotrexate	Sulfasalazine
Azathioprine	Hydroxychloroquine sulfate
Cyclophosphamide	Certolizumab pegol
Leflunomide	Golimumab
Anakinra	Tocilizumab

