4.4 Metrics and Variables

The primary outcome of interest is COVID-related hospitalization rate in study participants and matched controls. We list all potential covariates in two phases. Phase I covers historical data and Phase II includes post COVID-19 diagnosis information. Phase I historical data will be collected for both study participants and matched controls. Phase II post-COVID 19 diagnosis data has two parts: data elements to be collected for both study participants and matched controls (Phase II.A), and data elements to be collected for only study participants (Phase II.B).

Phase I - Historical data: Study participants and matched controls:

1. COVID-19-related information:

- Symptomatic or asymptomatic during COVID-19 test
- Number of COVID-19 cases per 10,000 people in the county of residence during COVID-19 test (if available)
- Number of COVID-19 deaths per 10,000 people in the county of residence during COVID-19 test (if available)

2. Demographic:

- Age as of 2020
- ZIP code of residence (may or may not be used for identifying matched controls)
- Urbanization of residence in a zip code level (urban, suburban, rural)
- Region/State of residence
- Race
- Gender
- Flag determining whether a patient resides in a nursing facility (or has been staying in a nursing facility currently) – determining patient does not live at home

3. Insurance:

- Line of business (should be mostly Medicare)
- Dual-eligibility status
- Continuous member enrollment in 2019
- Continuous member enrollment in 2020

3. Comorbidities in 2019:

- History of chronic kidney disease
- History of diabetes
- History of immunosuppressive disease
- History of cardiovascular disease
- History of hypertension
- History of chronic obstructive pulmonary disease/other chronic respiratory disease

- Elixhauser score for readmission
- Historical flag for all other associated comorbidities used in computing Elixhauser score (i.e., 29 categories like kidney disease, cancer etc.)

4. Immunosuppressive treatment

- History of receiving immunosuppressive treatment (6 months prior to date of COVID diagnosis)

Phase II.A: Post COVID-19 diagnosis data: Study participants and Matched controls

- Date of COVID-19 diagnosis test
- Type of COVID-19 diagnosis test (e.g., PCR, Antigen)
- Hospital admission date (if patient is hospitalized)
- Type of hospital admission (measuring level of trauma) (if available)
 - Through ER (if any)
 - With ICU transfer (if any)
 - With ventilation (if any)

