Commented [JAT20R19]: Agreed. We include obesity as a comorbidity in 4. Comorbidities in 2019 part below. This comorbidity is extracted from our claims data.

It makes perfect sense to include BMI, but we don't have this numerical value from the claims data and have very limited coverage from other data sources.

3. Insurance:

Variable	Data source for study participants	Data source for matched controls
Line of business		
Dual-eligibility status		
Continuous member enrollment in 2019	UHC claims	Optum EMR or UHC claims
Continuous member enrollment in 2020		
Continuous member enrollment in 2021 (up to available months)		

4. Comorbidities in 2019:

Variable	Data source for study participants	Data source for matched controls
Elixhauser score for readmission	UHC claims	Optum EMR or UHC claims
Historical flag for all associated comorbidities used in computing Elixhauser score*		

*: The 29 categories include diabetes, obesity, chronic pulmonary disease, congestive heart failure, etc. The full list is in Table A2 of Appendix 1.

Commented [WWY21]: Will comorbidities be looking only in 2019?

Commented [JAT22R21]: Yes, we chose the year 2019 because the year 2020 is a special year, and people tend to use healthcare less than usual. Besides, we assume that comorbidities listed here last to the end of our study or even longer given most of them are chronic (e.g. T2D, renal failure, congestive heart failure) and our study cohort is the Medicare Advantage cohort.

5. Immunosuppressive treatment

Variable	Data source for study participants	Data source for matched controls
History of receiving immunosuppressive treatment 6 months prior to date of COVID diagnosis*	UHC claims	Optum EMR or UHC claims

*: Please see the full list of immunosuppressive prescriptions in Table A3 of Appendix 1.

Phase II.A: Post COVID-19 diagnosis data: Study participants and Matched controls

Variable	Data source for study participants	Data source for matched controls
Date of COVID-19 admission (if hospitalized)		

CONFIDENTIAL

[Protocol number: UHG (J2X-NS-I002)] SAP [\[v.3\]](#)

ER flag (admitted from ER; if data is available)		
ICU flag (related to ICU transfer; if data is available)	BCRT	Optum EMR or BCRT
Ventilation flag (use of ventilation; if data is available)		
Diagnosis code – primary		
Diagnosis code – secondary		
Diagnosis code – tertiary		
Date of discharge (if applicable)		
Date of death (if applicable)		

Phase II.B: Post COVID-19 diagnosis data: Study participants only

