5.7 Prior Medication and Concomitant Therapy

According to the EUA, we consider immunosuppressive medications 6 months prior to date of COVID-19 diagnosis as a potential risk factor of COVID-19 hospitalization. Additional descriptive summaries on prior medications and concomitant therapies could be provided for study participants and matched controls if available.

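### The immunosuppressive-treatment flag rests on a closed drug list that omits systemic corticosteroids and other classes, and the protocol's separate immunosuppressive-disease covariate is no longer named in the SAP

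*SAP*

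**What the plan says.** **Role of the covariate.** SAP 5.7, citing the emergency use authorization (EUA), says "we consider immunosuppressive medications 6 months prior to date of COVID-19 diagnosis as a potential risk factor of COVID-19 hospitalization". The variable appears in mock Tables A4 (characteristics), A5 (risk-factor models), A8 and A8.2 (balance before and after propensity matching) and A11 (balance for double-score matching).

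**Definition.** SAP 4.7 gives a six-month look-back and sends the reader to the appendix: "Please see the full list of immunosuppressive prescriptions in Table A3 of Appendix 1". There the rule is "We identify immunosuppressive treatment by the following prescriptions in our claims data", followed by "Table A3. The list of immunosuppressive prescriptions". Among the 22 entries are "Hydroxychloroquine sulfate" and "Sulfasalazine". No rationale for the list is given.

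**Source.** SAP 4.7 names UHC claims for participants, but Optum EMR or UHC claims for controls.

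**Protocol counterpart.** Protocol 4.4 has two separate items: "History of immunosuppressive disease", under comorbidities in 2019, and "History of receiving immunosuppressive treatment (6 months prior to date of COVID diagnosis". SAP 4.7 keeps the treatment item and reduces comorbidities to the Elixhauser score and its 29 condition flags. SAP 5.14, the section for changes from the protocol, is marked not applicable.

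**The concern.** A matched comparison with external controls is only as good as the covariates it matches on. A patient who is immunosuppressed by an agent outside Table A3 is coded as not immunosuppressed. If such patients are more common in one group, matching on the flag leaves a difference in baseline hospitalization risk that is then read as a treatment effect.

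Nothing planned would expose this. Table A8.2 checks balance on the same flag. SAP 5.8.2 does not list immunosuppression among the potential unmeasured confounders. SAP 5.8.3 treats measurement error as random and negligible.

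A difference between the groups is plausible. Participants enroll themselves through an online platform and agree to use a symptom-tracking app (Protocol 5.7 and Appendix 1). Controls are symptomatic patients found in the EMR after seeking care (Protocol 5.3, SAP 4.4.1). The documents do not show which group would carry more immunosuppression.

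**Working it through.** **1. Table A3.** All 22 entries were read. They cover transplant drugs (for example cyclosporine, tacrolimus and the mycophenolates), antirheumatic drugs (for example methotrexate and leflunomide), cyclophosphamide, and biologics (for example infliximab, adalimumab and tocilizumab).
- Systemic corticosteroids, by drug name or class term: 0 of 22.
- B-cell-depleting antibodies: 0. JAK inhibitors: 0.
- Hydroxychloroquine and sulfasalazine: both present.

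**2. Protocol against SAP.**

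| Item | Protocol 4.4 | SAP 4.7 and Appendix 1 |
|---|---|---|
| Immunosuppressive treatment, prior 6 months | Listed, no drug list | Listed, defined by Table A3 |
| Immunosuppressive disease | Listed as its own item | Not named; absent from Tables A4, A5, A8 and A11 |
| Related condition flags | All Elixhauser conditions | Table A2: AIDS, lymphoma, solid tumor, metastatic cancer, rheumatoid/collagen vascular disease |

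Immune deficiency outside the Table A2 categories, such as primary immunodeficiency, has no visible place. Transplant status may be picked up indirectly through the transplant drugs. The Table A2 flags come from 2019 only, as a sponsor reply in the margin of SAP 4.7 confirms. The six-month drug flag is therefore the only recent measure.

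**3. Size.** The documents give no prevalence, risk ratio or accuracy for this flag, so there is no plan figure to reproduce and every input below is an assumption. Let p1 and p0 be the prevalence of unrecorded immunosuppression in participants and matched controls, and RR its risk ratio for hospitalization. With no treatment effect, the apparent risk ratio is

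B = [1 + p1(RR − 1)] / [1 + p0(RR − 1)].

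Assumed ranges: p1 2–5%, p0 5–8%, RR 1.5–2.5.

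| p1 | p0 | RR | B |
|---|---|---|---|
| 0.02 | 0.08 | 2.5 | 1.03 / 1.12 = 0.92 |
| 0.02 | 0.08 | 1.5 | 1.01 / 1.04 = 0.97 |
| 0.03 | 0.05 | 2.0 | 1.03 / 1.05 = 0.98 |
| 0.05 | 0.08 | 1.5 | 1.025 / 1.04 = 0.99 |
| 0.05 | 0.05 | any | 1.00 |

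The full range is 0.92–1.00. With the first row's prevalences exchanged, B = 1.12 / 1.03 = 1.09, so the sign reverses.

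**4. Cross-check with an explicit imperfect flag.** Suppose the groups are matched exactly on a flag with sensitivity 0.4 and specificity 1.0, true prevalence is 5% in participants and 10% in controls, and RR is 2.
- Flagged share among participants: 0.05 × 0.4 = 0.02. Controls are matched to the same share.
- Truly immunosuppressed among the unflagged: participants 0.03 / 0.98 = 0.0306; controls 0.06 / 0.96 = 0.0625.
- Relative baseline risk: participants 1 + 0.02 + 0.98 × 0.0306 = 1.050; controls 1 + 0.02 + 0.98 × 0.0625 = 1.081.
- Ratio: 1.050 / 1.081 = 0.97.

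With control prevalence 10–15%, sensitivity 0.4–0.7, specificity 0.96–1.0 and RR 1.5–2.0, the residual ratio runs from 0.93 to 0.99. Without matching on this factor it would be 0.91–0.98. With equal true prevalence it is 1.00 however poor the flag.

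**5. Yardstick.** SAP 4.4.2 plans to detect a fall from 15% to 10%, a risk ratio of 10 / 15 = 0.67. At the worst corner in step 3, a null effect would look like a fall from 15% to 15% × 0.92 = 13.8%.

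**The case against.** The strongest case on the other side has six parts.

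- **The flag is not a wrong variable.** Most entries are undisputed immunosuppressants. A reader might infer that the trial matches on the wrong quantity altogether. The documents do not support that: the list is incomplete, not misdirected. This stands.
- **Disease content is not lost.** A reader might also infer that AIDS is the only related condition left. Table A2 keeps lymphoma, cancers and rheumatoid/collagen vascular disease. It also has chronic pulmonary disease, so two likely indications for steroids are candidate matching covariates. This stands, but a 2019 lung or joint diagnosis does not separate current steroid users from non-users.
- **Other routes exist.** SAP 5.8.1.1 promises all risk variables identified by the drug's manufacturer, and SAP 5.2 promises all risk factors that qualified patients for entry. Neither gives another operational definition of immunosuppressive treatment, so Table A3 remains the only one.
- **Use is conditional.** Whether the flag enters the propensity model depends on the selection in SAP 5.8.1.1, and Table A5 calls its variables subject to change. This stands.
- **Section 5.14 concerns analyses, and these are only potential covariates.** That is a fair reading, and the omission may be a consolidation into Elixhauser flags. It is still a consolidation with one item unmapped, and nothing says so.
- **Which drugs belong is outside knowledge.** The documents do not reproduce the EUA definition. That corticosteroids are immunosuppressive is general pharmacology. The view that hydroxychloroquine and sulfasalazine should not count is more debatable, so the documents give no ground for simply deleting them.

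**Conclusion.** The point holds as a request for a better-defined covariate. Table A3 is a closed, unexplained list that leaves out systemic corticosteroids and other immunosuppressant classes. A named protocol covariate is missing from the SAP with no record of the change. The planned balance checks cannot detect what the flag misses.

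The effect on the primary result is likely to be modest: a spurious risk ratio of 0.92–1.00 under the assumptions in step 3 of the working, against a planned effect of 0.67. This could not by itself produce an effect of the planned size, but it would add to any other bias in the same direction. It requires that true immunosuppression differ between groups within levels of the other matched covariates. Step 3 gives no credit for balance already gained on related conditions. The direction is not known.

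**What to change.** Before outcome data are accessed:

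1. Restore the protocol's immunosuppressive-disease history as a diagnosis-code flag in SAP 4.7 and Tables A4, A5, A8 and A11, or record its removal in 5.14 with the reason.
2. Extend Table A3 with systemic corticosteroids, under a sustained-supply rule so that short courses do not set the flag (for example a minimum cumulative days' supply in the six months), and with the other omitted immunosuppressant classes.
3. Keep hydroxychloroquine and sulfasalazine as a separate flag, or test their exclusion in a sensitivity analysis.
4. Apply the same code list to the same source type in both groups. SAP 5.1.1 restricts the analysis populations to UHC members, so claims should be available on both sides.

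The cost is a longer code list, a little programming in data already held, and one more matching covariate.
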